9.1.4 Packaging and Labeling

All study drug supplies will be provided by the Sponsor (or third-party designee).

Zavegeptan 25 mg SGC or matching placebo will be packaged in blister packs and will hold 48 capsules that are heat sealed into a wallet; 8 wallets will be placed into a subject specific carton/kit. The kits and wallets will have a unique identifier (kit/wallet number) included on the label. Each wallet will cover 4 days of AM (6 capsules) and PM (6 capsules) dosing. Please reference the Pharmacy Manual for additional details.

An interactive web-based response system (IWRS) system will be used to assign kits/wallets by a unique identifier to be dispensed to the subject.

The blister packs will not require labeling, but kits/wallets will have a full clinical label on the outside and will contain information required by local regulations.

9.2 Non-Investigational Product

Not applicable.

9.3 Dosage and Administration

After subjects have met all eligibility requirements in Part 1 and completed the rest/washout period, they will be randomized in a 1:1 ratio to receive zavegeptan or placebo. Investigational product will be dispensed at Visit 5. Subjects will take 6 25-mg capsules BID, in the morning and evening, for at least 28 days. Subjects should dose consistently at the same time of day, preferably in the morning and evening. Each dose of study drug should be taken while fasting (e.g., at least 1 hour before breakfast/first meal of the day for the first dose, and at least 4 hours after the previous meal for the second dose). Subjects should not consume food other than water for 1 hour after dosing.

9.3.1 Method of Study Treatment Assignment

After informed consent is obtained and study criteria is met at screening, the investigator or designee will obtain a subject number and treatment assignment via an IWRS. The IWRS system will assign a subject specific blinded study treatment kit that will contain 8 wallets, enough for the total treatment duration, to be dispensed to subjects. Once the kits/wallets have been assigned, they cannot be dispensed to another study subject. Sites will be responsible for recording the kit and wallet numbers dispensed to the subject on the Drug Accountability Form provided in the regulatory binder, as well as ensure appropriate documentation of dispensation in the subject's medical record.

Once a subject completes the study, or if a subject is discontinued early from the study, the investigator or designee must access the IWRS to document discontinuation of the subject from study participation.

9.3.2 Blinding

After the subject's treatment assignment number is obtained from the IWRS, the number will be provided to the investigator or designee at the study center who is responsible for distribution of study treatment. The IP and placebo will be identical in appearance and labeled in a blinded manner. No study site personnel, subject, Sponsor personnel, or Sponsor designee will be unblinded to treatment assignment throughout the duration of the study unless unblinding is required. If an investigator becomes unblinded to a given subject's study treatment, that subject will be discontinued from the study unless there are ethical reasons for the subject not to be discontinued; approval from the Sponsor's medical monitor must be obtained in such instances.

In the event that an emergency unblinding is required for a subject because of an AE or concerns for the subject's safety or wellbeing, the investigator may break the randomization code for the subject via the IWRS. The investigator is responsible for notifying the medical monitor and/or Sponsor of such an event as soon as possible. The unblinding and its cause will also be documented in the eCRF.

9.4 Accountability and Compliance

The blinded pharmacist or other designated individual at the study site will maintain records of study treatment delivered, manage inventory at the site, distribution and use by each subject, and the return of materials to the Sponsor for storage or disposal. These records should include dates, quantities, lot/kit/wallet numbers, expiration dates, in-clinic temperature log, and unique code numbers assigned to the product and study subjects. If it is site policy to destroy study drug on site, it is the investigator's responsibility to ensure that arrangements have been made for the disposal, procedures for proper disposal have been established according to the applicable regulations, guidelines and institutional procedures, and appropriate records of the disposal have been documented. The unused study drugs can only be destroyed after being inspected and reconciled by the responsible Study Monitor or the Sponsor's designee.

At each visit after initiation of treatment, study site personnel will record compliance of the subject with the assigned regimen. The same study drug kits/wallets dispensed at Visit 5 will be used for study drug dosing through Visit 8. Subjects will be instructed to bring kits/wallets containing unused/partially used/empty wallets back for inspection at each study visit, or unscheduled site visit, if applicable. Subjects are to be reminded of the importance of compliance with their assigned regimen, with an emphasis on taking their study drug on schedule and maintaining the prescribed interval between doses.

Investigative site staff will maintain records that adequately document that the subjects were provided with the correct study treatment kits/wallets and reconcile the products received from the drug dispensing center. Investigational product will not be returned to the Sponsor until accountability is completed at the end of the study and all wallets and IP documentation has been fully monitored.

Medication kits/wallets must be returned to the site at the end of the trial, as compliance will be assessed by capsule counts. Subjects have to be counseled on the importance of taking the study drug as directed. If poor compliance continues, (i.e., more than 1 missed dose in a week or cancellation of any site visit) discontinuation of the subject from the trial should be considered. If there are concerns about subject compliance, contact the clinical research organization (CRO)/Sponsor for guidance.

The morning dose of study drug treatment at Visits 5 through 8 will be supervised for compliance by study site personnel.

9.5 Dosage Modification

Dose modification is not allowed in this trial.

9.6 Prohibited and Concomitant Medications

All concomitant medication and therapy, including vaccines, used from 30 days before trial participation through end of study should be documented on the eCRF. This includes both prescription and non-prescription drugs.

The use of any CGRP receptor antagonist treatment or CGRP antibody is prohibited from 6 months prior to the screening until study completion/early termination.

Chronic use of any other medication for treatment of allergic lung disease other than short-acting β 2-agonists is prohibited.

See [Table 9-1](#) and [Table 9-2](#) for prohibited and restricted medications, respectively.

Table 9-1. Prohibited Medications

Prohibited medications	Restriction window/Washout
CGRP-targeting medications (prophylactic or acute)	6 months prior to Screening
Anti-IgE therapy	5 months before Screening
Allergy immunotherapy	4 months before Screening
Investigational drug	30 days or 5 half-lives (whichever is longer) before Screening
Systemic corticosteroids Inhaled corticosteroids Topical nasal corticosteroids Immunosuppressives Anticoagulants Theophylline Nedocromil or cromoglycate Modafinil St. John's wort	28 days before Screening
Atypical antipsychotics such as aripiprazole, olanzapine, quetiapine, ziprasidone, or risperidone	12 months prior to Screening
Mood stabilizers such as lithium, lamotrigine or divalproex/valproic acid/valproate	12 months prior to Screening
Strong cytochrome P450 3A4 (CYP3A4) inhibitors or inducers (list below is not all-inclusive): Inhibitors: clarithromycin, cobicistat, conivaptan, danoprevir and ritonavir, elvitegravir and ritonavir, indinavir and ritonavir, itraconazole, ketoconazole, lopinavir and ritonavir, nefazodone, neflunavir, paritaprevir and	28 days or 5 half-lives (whichever is longer) before Screening If use of a strong CYP3A4 inhibitor or inducer is required during the trial, dosing should be stopped and should not start again until 14 days after the last dose of the strong CYP3A4 inhibitor/inducer

Prohibited medications	Restriction window/Washout
ritonavir and (ombitasvir and/or dasabuvir), posaconazole, ritonavir, saquinavir and ritonavir, tipranavir and ritonavir, troleandomycin, voriconazole Inducers: apalutamide, carbamazepine, phenobarbital, phenytoin, rifampin, rifapentine, St. John's wort	
Potent P-glycoprotein (P-gp) inhibitors or inducers (list below is not all-inclusive): Inhibitors: amiodarone, clarithromycin, cyclosporine, dronedarone, itraconazole, lapatinib, propafenone, quinidine, ritonavir, verapamil Inducers: carbamazepine, phenobarbital, phenytoin, rifampin, St. John's wort	28 days or 5 half-lives (whichever is longer) before Screening If use of potent P-gp inhibitor or inducer is required during the trial, dosing should be stopped and should not start again until 14 days after the last dose of potent P-gp inhibitor/inducer
Leukotriene modifiers Long and moderate-acting beta-agonists Long-acting anticholinergics Antimuscarinics	14 days before Screening
Non-steroidal anti-inflammatory drugs	3 days before Screening

Sources: [US FDA Table of Substrates, Inhibitors and Inducers](#); Hachad et al., 2010

Table 9-2. Restricted Medications

Restricted Medications	Restriction Window
Short-acting beta2 agonists Short-acting anticholinergics	8 hours before all study visits
Aspirin	7 days before allergen challenge and dosing
Short-acting antihistamines	3 days before allergen challenges
Intermediate-acting antihistamines	4 days before skin testing and allergen challenges
Long-acting antihistamines	9 days before skin testing and allergen challenges
Acetaminophen	Limited to no more than 1000 mg/day for a maximum of 2 consecutive days
Inhaled corticosteroids Systemic corticosteroids	If rescue treatment is required during the screening period, 1-week washout from acute dosing
Methlyxanthines	4 hours before spirometry
Long-acting beta-agonist Leukotriene modifiers	If rescue treatment is required during the screening period, 2-week washout from acute dosing
OTC drugs, including cold and allergy medications	72 hours prior to methacholine and allergen challenges

Lifestyle restrictions include:

- No alcohol within 48 hours prior to study visits.
- No strenuous exercise within 8 hours of study visits.
- No caffeine-containing products or medications for 12 hours prior to methacholine and allergen challenges.

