c A full examination will be performed at screening and at follow-up. BMI will be calculated at Screening Visit 1.

d Serum pregnancy test conducted at screening; urine pregnancy testing at all other visits as indicated. Results of the pregnancy test are required before dosing. Source documents should document that WOCBP agree to use 2 effective forms of contraception and men with WOCBP partners agree to use condoms with a spermicide during treatment.

e Allergen skin titration test can be performed at either Visit 1 or Visit 2 to allow for flexibility.

f After randomization, daily dosing in Part 2 from Visit 5 through Visit 8, inclusive. No onsite visit required after start of study medication at Visit 5 to start of allergen triad (Visit 6). Every effort should be made to conduct the study visits within the specified windows in Part 2. However, if necessary due to local COVID-19 safety requirements, visits may be performed outside of these windows in order to minimize any potential risks to subject safety and to comply with governmental and institutional guidance.

g Subjects should dose consistently at the same time of day, preferably in the morning and evening. Each dose of study drug should be taken while fasting (e.g., at least 1 h before breakfast/first meal of the day for the first dose, and at least 4 h after the previous meal for the second dose). Subjects should not consume food other than water for 1 h after dosing.

h Subjects will be asked to complete a daily diary to capture date and times of both meals and study drug administration.

i Pharmacokinetic sampling to be conducted predose on Visits 6, 7, and 8, and additionally at Visit 7 at approximately 1 (+ 0.5 h) h and 3 (+/- 0.5 h) h postdose. Subjects should be instructed to hold their daily dose of study drug on the morning of Visits 6, 7, and 8 and arrive at the clinic after an overnight fast. Exact times of dosing and PK sample collection will be documented.

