10.2.1 Part 1 – Screening Period

The screening period includes screening procedures to determine initial eligibility (Visit 1) and methacholine and allergen challenge assessments (Visits 2, 3, and 4). The subject must undergo and pass all eligibility assessments in order to participate in the Part 2 dosing phase of the study.

Visit 1: Day -29 to Day -16 (onsite)

- Written informed consent will be obtained.
- Inclusion/exclusion will be assessed.
- Demographics, medical history, and medication history will be obtained and recorded.
- Concomitant and ongoing medications will be recorded.
- Vital signs will be measured (sitting blood pressure [systolic and diastolic blood pressure], heart rate, respiratory rate, body temperature).
- A physical examination will be performed, including BMI.
- A resting 12-lead ECG will be performed; subject should be in a resting, supine, or semi-recumbent position for at least 5 minutes.
- Spirometry measurements will be performed.
- WOCBP will undergo serum pregnancy testing. This pregnancy test must be negative in order for the subject to participate in the study and receive drug. WOCBP must await the results of the pregnancy test before receiving drug. WOCBP and men with partners of

childbearing potential must also use effective contraception during treatment; see [Section 8.3](#) for details.

- Blood samples for hematology and chemistry will be obtained; urine samples will be obtained for urinalysis and drug testing.
- Allergic status will be documented by skin prick testing against common airborne allergens (e.g., cat, dust mite, grass, pollen).
- An S-STS will be conducted; subject score must be 0 to be eligible to enroll.

Visits 2, 3, and 4: ~Days -15, -14, -13

- Inclusion/exclusion will be assessed.
- AEs, concomitant medications, and ongoing medications will be recorded.
- Spirometry measurements will be taken.

3-Day Allergen Triad

Visit 2: Allergen skin titration (only if procedure was not previously performed at Visit 1), methacholine challenge, and sputum induction will be performed. At approximately 24 hours before the allergen challenge, subjects will be assessed for AHR by methacholine challenge (methacholine PC₂₀ must be \leq 16 mg/mL) and a sputum sample will be induced.

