11.1.4 Skin Testing

An allergy skin test, also called a skin prick test, will be used to determine the allergen that is given to each patient in the inhalation allergen challenge. It is performed by applying an extract of an allergen to the skin, scratching or pricking the skin to allow exposure, and then evaluating the local reaction in the skin. Standard allergen extracts for the following allergens will include, but are not limited to, ragweed, tree mix, grass mix, dog, cat, horse, feathers, dust mites (*Dermatophagoides farinae* and *D. pteronyssinus*), Alternaria, and Aspergillus. A positive control (1 mg/mL histamine) and a negative control (diluent) are applied to the skin. If an allergen provokes an allergic reaction, a raised itchy bump (wheal) and redness (flare) develops. The size of the wheal (the raised area, not the redness) will be measured and recorded with a ruler in millimeters in the horizontal and vertical directions, perpendicular to each other after approximately 15 minutes. The size of the wheal for each antigen will be recorded on the Skin Test Form, along with any observed adverse reaction or event and any actions taken. A reaction greater than 2×2 mm will be regarded as positive, provided that the positive and negative controls are appropriately positive (histamine) and negative (diluent), respectively. The investigator will choose an allergen for inhalation on the basis of the largest skin response. This procedure will be completed in accordance with the CIC allergy skin testing by epicutaneous method (prick) SOP at McMaster University (Hamilton, Ontario, Canada).

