11.1.5 Allergen Skin Titration

An allergy skin titration test is used to identify the lowest titration of allergen that causes a skin wheal at least 2×2 mm in size. It is performed by applying serial dilutions of a selected allergen extract to the skin, scratching or pricking the skin to allow exposure, and then measuring the skin's reaction with a ruler. The diameter of each wheal is measured in 2 perpendicular directions

after 10 minutes. The average wheal diameter for each dilution in the horizontal and vertical directions is recorded on the worksheet (i.e., 4×3 mm). The weakest dilution of allergen that produces an average wheal of at least 2×2 mm is the “skin test endpoint.” This measurement is used to calculate the starting allergen dose for inhalation.

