Allergy skin titration testing will be performed at Visit 1 and Visit 2. It will identify the lowest titration of allergen that causes a skin wheal at least 2 x 2 mm in size. The diameter of each wheal is measured in 2 perpendicular directions after 10 minutes. The average wheal diameter for each dilution in the horizontal and vertical directions is recorded. The weakest dilution of allergen that produces an average wheal of at least 2 x 2 mm is the "skin test endpoint." This measurement is used to calculate the starting allergen dose for inhalation.

This document is confidential.

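### Table 9-2 sets no hold on short-acting antihistamines before skin testing, and two other medication entries conflict with Table 9-1 or SAP Appendix A

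*Protocol*

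**What the plan says.** **Antihistamines (protocol Section 9.6, Table 9-2).** There are three rows:
- short-acting: "3 days before allergen challenges"
- intermediate-acting: "4 days before skin testing and allergen challenges"
- long-acting: "9 days before skin testing and allergen challenges"

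A separate row holds over-the-counter cold and allergy products for 72 hours before methacholine and allergen challenges. It does not name skin testing either.

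**Skin tests.** Table 10-1 puts the prick test at Visit 1 (Day -29 to -16). Footnote e says of titration: "Allergen skin titration test can be performed at either Visit 1 or Visit 2 to allow for flexibility". Section 10.2.1 lists it at Visit 2 only as a fallback, and SAP Section 8 says "Allergy skin titration testing will be performed at Visit 1 and Visit 2". Under Section 11.1.4 the largest prick response decides which allergen is inhaled. Of the titration result, Section 11.1.5 says: "This measurement is used to calculate the starting allergen dose for inhalation".

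**Antimuscarinics.** Table 9-1 prohibits them for 14 days before Screening with no qualifier, next to long-acting anticholinergics. SAP Appendix A repeats the two as separate bullets. Table 9-2 allows short-acting anticholinergics with an 8-hour hold before visits.

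**Screening rescue.** Table 9-2 provides for corticosteroid rescue (inhaled or systemic, 1-week washout) and for long-acting beta-agonist or leukotriene-modifier rescue (2-week washout). Appendix A lists the same classes as relevant deviations when used from consent onwards, with no separate treatment of rescue.

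**The concern.** Two of the three antihistamine rows name skin testing, so the drafters had it in mind, and the third row leaves it out. A recent dose can shrink a wheal. At the prick test, that could hide a positive response or change which allergen ranks largest. At titration, a weak dilution that would have reached 2 × 2 mm may fail to do so. The subject then looks less sensitive, and the expected direction is a higher starting dose for inhalation. That is a matter of challenge safety and of valid allergen selection.

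The other two mismatches concern consistency. One drug class is prohibited in one table and allowed with a hold in another, so sites may differ on eligibility, and use that respects the hold is counted as a deviation. Likewise, a subject given rescue as Table 9-2 foresees is tabulated with prohibited-drug users, under a heading that SAP Section 7.4 reserves for deviations that may bear on the reading of the results.

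**Working it through.** No figure in the plan needs reproducing. The check is a comparison of the tables plus day counts on the nominal schedule, ignoring visit windows.

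**1. What the existing holds guarantee before a skin test.** The allergen challenge is Visit 3 (Day -14) and the methacholine test is Visit 2 (Day -15).
- 3-day row: -14 - 3 = Day -17.
- 72-hour over-the-counter row, counted from the earlier methacholine test: -15 - 3 = Day -18.
- Guaranteed drug-free days = max(0, skin-test day - day the hold starts).

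| Skin-test day | From the 3-day row | From the over-the-counter row, where it applies |
|---|---|---|
| -29 to -18 (Visit 1) | 0 | 0 |
| -17 (Visit 1) | 0 | 1 |
| -16 (Visit 1) | 1 | 2 |
| -15 (Visit 2) | 2 | 3 |

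For example, take a dose on a Day -20 Visit 1. It is 6 days before the challenge (more than 3) and 5 days before the methacholine test (more than 72 hours). Neither row is breached, yet both skin tests can be done that day. The same holds for any Visit 1 on Day -19 or earlier, where the distances are at least 5 and 4 days. That covers 11 of the 14 nominal Visit 1 days (29 - 19 + 1 = 11; 29 - 16 + 1 = 14). At Visit 2 the existing holds already give 2 or 3 days, so the gap is essentially the Visit 1 route.

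The shift in starting dose cannot be computed, because the formula is cited but not given.

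**2. Antimuscarinics.** The 8-hour row has two drug entries. Short-acting beta2-agonists are not caught by Appendix A, because the beta-agonist entries in Table 9-1 and Appendix A are qualified by duration of action. Short-acting anticholinergics are antimuscarinics, so the unqualified entry catches them: 1 of 2.

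**3. Rescue.** Table 9-2 names four rescue entries: inhaled corticosteroids, systemic corticosteroids, long-acting beta-agonist and leukotriene modifiers. All 4 appear in Appendix A. Consent is at Visit 1, so all rescue after consent within screening falls inside the Appendix A rule. Table 9-2 does not say what the washout must come before: the next challenge, or the first dose.

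**4. Which analyses are touched.** SAP Section 5.1 defines mITT by at least one dose and at least one post-baseline late-response assessment. No rule removes a subject for these deviations. The effect is on the Section 7.4 deviation table and listing.

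**The case against.** **On antihistamines**, the best defence is that the plan already has safeguards. A prick result counts only "provided that the positive and negative controls are appropriately positive (histamine) and negative (diluent), respectively", so a strongly blunted subject should be exposed at the same visit. Titration sets only the start of a challenge that rises in doubling steps with FEV1 read at 10 minutes. A site procedure that we cannot see may also cover antihistamines. This stands in part. However, Section 11.1.4 gives no threshold for an adequate histamine wheal, Section 11.1.5 names no control for titration, and the doubling steps still begin from whatever start was calculated. One could also read the challenge wording as including skin tests, but the neighbouring rows name the two separately.

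**On antimuscarinics**, a reader would normally let the specific short-acting row govern, and the sponsor may have meant long-acting agents only. That is plausible, but the separate Appendix A bullet does not say so.

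**On rescue**, the objection is stronger. A reader might infer that the rule gives a deviation to a compliant subject who would otherwise have none, for instance one rescued at Visit 3 and dosed on nominal Day 1. The documents do not support that example. Visit 4 (Day -13) to Day 1 is 13 days, because SAP Section 6.2 has no Day 0, so this subject already breaches the separate Appendix A line for a Visit 4 washout outside 2 to 4 weeks. If the rescue washout must precede the next challenge, the subject also breached Table 9-2, since Visit 4 is one day later.

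A reader might also infer that screening rescue should simply be exempted. That goes too far. Rescue between Visits 3 and 4 comes just before the methacholine test that enters the baseline PC20 shift (Visit 4 minus Visit 2), the covariate in SAP Section 8.2.2. Those subjects should remain identifiable.

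**Conclusion.** The antihistamine gap is real and minor. Two classes have 4- and 9-day holds before skin testing; the short-acting class has none, and the challenge-based holds give no protection on most nominal Visit 1 days. The clinical size is unknown. The conclusion assumes only that a recent dose can reduce a wheal.

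The antimuscarinic overlap is real and rests on class meaning. Its reach is small: Section 9.6 bars chronic use, and inclusion criterion 1 limits bronchodilator use to fewer than 2 per week.

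The rescue mismatch is real as a matter of classification. The documents give no count of affected subjects and support no percentage for it.

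A reader might infer that the efficacy result is at risk. It is not. Skin testing precedes randomisation, the same final three allergen doses are used at both challenges, and neither the mITT set nor the primary model depends on these entries.

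**What to change.** 1. **Table 9-2, short-acting antihistamines:** insert *skin testing and* before *allergen challenges*, keeping 3 days. This needs no new visit. Titration may already move to Visit 2, and protocol Section 7.1 and SAP Section 8 also allow the prick test there.
2. **Table 9-1 and SAP Appendix A:** replace the unqualified entry with *Antimuscarinics other than short-acting inhaled anticholinergics (see Table 9-2)*.
3. **SAP Appendix A, rescue:** tabulate screening rescue that meets the Table 9-2 washout as its own subcategory, separate from prohibited use. State whether the washout must be complete before the next methacholine or allergen challenge, or before the first dose. Under either choice, rescue between Visits 3 and 4 stays visible.

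Items 1 and 2 cost a phrase in each entry. Item 3 costs more. Relevant deviations are programmed from the database, so it needs a rescue indicator and a defined washout endpoint, and the documents do not show that the indicator is collected. If it is not, blinded review of the non-study medication listing could assign the subcategory.

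The study stopped in 1Q2023 for low enrolment, so only the Appendix A edits can still change an output. The protocol-table edits matter if the wording is reused.
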